Once the protocol has been approved by the Institutional Review Board (IRB), I will not modify this protocol without obtaining the prior approval of the Sponsor and of the IRB. I will submit the protocol modifications and/or any informed consent form (ICF) modifications to the Sponsor and the IRB, and approval will be obtained before any modifications are implemented. I understand the protocol and will work according to it, the principles of Good Clinical Practice [GCP; current International Council for Harmonisation (ICH) guidelines], and the Declaration of Helsinki (1964) including all amendments up to and including the October 2013 revision.

Principal Investigator Name	Signature	Date	

SYNOPSIS

Title	T
1 lue	A Placebo-controlled, Multi-center, Randomized, Phase 2b Study to
	Evaluate the Efficacy and Safety of ORMD-0801 in Type 2 Diabetes
	Mellitus Patients with Inadequate Glycemic Control on Oral Therapy
Indication	Type 2 Diabetes Mellitus (T2DM)
Clinical Phase	Phase 2b
Study Treatment	ORMD-0801 (insulin)
Dose	Cohort A: Begin at 16 mg/dose, titrate to 24 mg/dose, then titrate to 32
	mg/dose
	Cohort B: 8 mg/dose or 16 mg/dose
Dosage Regimen	Cohort A: QHS, BID, or TID
	Cohort B: QHS or BID
Formulation	Soft gel capsule [SBTI, disodium EDTA, fish oil, aerosil, and Tween 80]
Mode of	Oral
Administration	
Primary Objective	To compare the efficacy of ORMD-0801 to placebo in improving
	glycemic control in T2DM subjects inadequately controlled on oral
~ -	therapy based on HbA1C.
Secondary	To assess the safety of repeat administration of ORMD-0801 in T2DM
Objective	subjects inadequately controlled on oral therapy
Total Sample Size	Approximately 360 adult male and female subjects age 18 and older with T2DM.
Study Design	This study is designed to explore efficacy of ORMD-0801 when given in different regimens across a dose range for up to 12 weeks in subjects
	with type 2 diabetes mellitus (T2DM). Approximately 360 subjects with T2DM will initially undergo a 2-week, single-blind placebo run-in
	period (Visits 1 and 2), followed by a 12-week treatment period (Visits 3 through 9). For Cohort A, the total 12-week treatment period will
	include a Part 1"dose escalation" interval (2 weeks, Visits 3 and 4) and
	a Part 2 stable dose "maintenance" interval (10 weeks, Visits 5 through
	9). The stable dose interval will be sufficient to allow for a robust
	assessment of treatment effect based on the mean change from baseline
	in HbA1C (A1C). For Cohort B, the total 12-week treatment period will include a stable dosing period for both Part 1 (2 weeks, Visits 3
	and 4) and Part 2 (10 weeks, Visits 5 through 9).
	Single-Blind Placebo Run-in:
	During the placebo run-in period subjects will self- administer blinded
	placebo study medication at night prior to bedtime (@10 PM \pm 90
	minutes each night, no sooner than 2 hours after dinner). Outpatient
	glycemic levels and adverse events will be measured using self-
	monitored blood glucose (SMBG) and recorded in a diary.
	Treatment Period:
	. •

Cohort A:

Of the total 360 subjects, 265 will be randomized to one of the following four treatment arms:

- 1) ORMD-0801 once daily QHS: dosed in the evening prior to bedtime (@ 10 PM ± 90 minutes)
- 2) ORMD-0801 twice daily BID: dosed in the evening prior to bedtime (@ $10 \text{ PM} \pm 90 \text{ minutes}$) and 30-45 minutes prior to breakfast.
- 3) ORMD-0801 three times daily TID: dosed in the evening prior to bedtime (@ $10 \text{ PM} \pm 90 \text{ minutes}$) and 30-45 minutes prior to breakfast and lunch.
- 4) Matched Placebo (either QHS, BID, or TID)

In addition, per FDA request, the remaining 20 subjects will receive excipient matched placebo in a non-randomized single-blind fashion, TID, according to the same schedule as described above.

Cohort B:

Of the total 360 subjects, 75 will be randomized to one of the following five treatment arms:

- 1) ORMD-0801 8 mg once daily QHS: dosed in the evening prior to bedtime (@ 10 PM ± 90 minutes)
- 2) ORMD-0801 8 mg twice daily BID: dosed in the evening prior to bedtime (@ $10 \text{ PM} \pm 90 \text{ minutes}$) and 30-45 minutes prior to breakfast.
- 3) ORMD-0801 16 mg once daily QHS: dosed in the evening prior to bedtime (@ 10 PM \pm 90 minutes)
- 4) ORMD-0801 16 mg twice daily BID: dosed in the evening prior to bedtime (@ $10 \text{ PM} \pm 90 \text{ minutes}$) and 30-45 minutes prior to breakfast.
- 5) Excipient matched placebo once daily QHS: dosed in the evening prior to bedtime (@, 10 PM ± 90 minutes)

Part 1:

Cohort A

In the first two weeks of active treatment (Part 1) subjects will receive double-blind therapy according to their randomized regimen (placebo or ORMD-0801) to be taken QHS, BID or TID. Subjects will undergo a step-wise dose escalation from a starting dose of 16 mg (Visit 3), to 24 mg (Visit 4), to a top dose of 32 mg (Visit 5 onward). Subjects will then enter Part 2.

Cohort B

	In the first two weeks of active treatment (Part 1) subjects will receive double-blind therapy according to their randomized regimen (ORMD-0801 8 mg or 16 mg, or excipient matched placebo) to be taken QHS or BID. Subjects will then enter Part 2 at the same dose and regimen administered in Part 1. Part 2:
	During Part 2, subjects will remain on fixed doses of ORMD-0801 (or placebo) for 10 weeks. Doses will not be adjusted unless clinically indicated for adverse events or hypoglycemia. Overall glycemia will be measured by A1C at baseline and over 12 weeks of treatment.
	Additional measures will include fasting plasma glucose (FPG) drawn at clinic visits, outpatient SMBG values and adverse events recorded in the diary. Subjects will undergo blinded continuous glucose monitoring (CGM) for 2 weeks at baseline (on at Visit 1, off at Visit 3) and end-of-study (on at Visit 8, off at Visit 9). Standardized Mixed Meal Tolerance Testing (MMTT) will be performed at baseline (Visit 3) and at end-of-study (Visit 9). A1C will also be measured at intervals.
	Throughout the 12-week treatment period, subjects will be monitored and may be considered for "rescue" in case of persistent symptomatic hyperglycemia (see Rescue Criteria) to restore adequate glycemic control.
Primary Endpoint	 Mean change in HbA1C from baseline to Week 12 (Visit 9, Part 2 Week 10) of the treatment period.
Secondary Endpoints	 Means and mean changes from baseline over time for HbA1C and FPG. Change from baseline to Week 12 (Visit 9, Part 2 Week 10) in postprandial glucose (PPG) parameters during a MMTT, including AUC₀₋₆₀, AUC₀₋₁₂₀, and 1 & 2-hour PPG absolute levels and excursions.
	 Changes from baseline in glycemic parameters measured using outpatient CGM. Change in weight from baseline to Week 12 (Visit 9, Part 2 Week 10) of the treatment period. Proportion of subjects requiring glycemic rescue therapy during
	 the treatment period. Safety assessed by adverse event reporting including adverse events of special significance such as hypoglycemia.
Exploratory Endpoints	Patient reported outcomes, by Diabetes Treatment Satisfaction Questionnaire _{status} (DTSQ _s) and Questionnaire _{change} (DTSQc) score over 12 weeks.
Duration of Participation	Subjects will be evaluated for participation in the study during a 1 to 3-week Screening period. Following Screening, eligible subjects will

begin a 2-week single-blind placebo run-in to evaluate compliance with the study procedures and assessment of baseline glycemic control. The double-blind active treatment phase will last a total of 12 weeks. A follow-up visit is required two weeks after the end of Part 2. The total length of participation is approximately 15-17 weeks depending on Screening time.

Subject Selection Criteria

Inclusion

- 1. Male and female subjects aged 18 and older.
- 2. Established diagnosis of T2DM for at least 6 months prior to Screening, with an HbA1C > 7.5%.
- 3. Stable dose of metformin (at least 1500 mg or maximal tolerated dose)/oral antidiabetic (OAD) for a period of at least 3 months prior to Screening.
- 4. Taking metformin only or metformin in addition to no more than two of the following: SU, DPP-4, SGLT-2, or TZD.
- 5. Body mass index (BMI) up to 40 kg/m² at Screening and stable weight, with no more than 5 kg gain or loss in the 3 months prior to Screening.
- 6. Renal function eGFR $> 30 \text{ ml/min/1.73 m}^2$
- 7. Females of childbearing potential must have a negative serum pregnancy test result at Screening.
- 8. Females who are are not of childbearing potential are defined as:
 - a. post-menopausal (defined as at least 12 months with no menses in women ≥45 years of age) or
 - b. has had a hysterectomy and/or bilateral oophorectomy, or had bilateral tubal ligation or occlusion at least 6 weeks prior to Screening
- 9. Subjects who are of childbearing potential must:
 - a. agree to remain abstinent from heterosexual activity[†] or agree to use (or have their partner use) acceptable contraception to prevent pregnancy within the projected duration of the trial and for 14 days after the last dose of blinded investigational product. Two methods of contraception will be used to avoid pregnancy. Acceptable combinations of methods include:
 - i. Use of one of the following double-barrier methods: diaphragm with spermicide and a condom; cervical cap and a condom; or a contraceptive sponge and condom
 - ii. Use of hormonal contraception (any registered and marketed contraceptive agent that contains an estrogen and/or a progestational agent [including oral, subcutaneous, intrauterine and

- intramuscular agents, and cutaneous patch]) with one of the following: diaphragm with spermicide; cervical cap; contraceptive sponge; condom; vasectomy; or IUD.
- iii. Use of an IUD with one of the following: condom; diaphragm with spermicide; contraceptive sponge; vasectomy; or hormonal contraception (see above).
- iv. Vasectomy with one of the following: diaphragm with spermicide; cervical cap; contraceptive sponge; condom; IUD; or hormonal contraception (see above).

[†]Abstinence can be used as the sole method of contraception if it is in line with the subject's preferred and usual lifestyle and if considered acceptable by local regulatory agencies and ethics committees. Periodic abstinence (e.g., calendar, ovulation, sympto-thermal, post-ovulation methods, etc.) and withdrawal are not acceptable methods of contraception.

Exclusion criteria

- 1. Subjects with insulin-dependent diabetes
 - a. has a history of type 1 diabetes mellitus or a history of ketoacidosis, or subject is assessed by the investigator as possibly having type 1 diabetes mellitus confirmed by a C-peptide <0.7 ng/mL (0.23 nmol/L).
 - b. has a history of other specific types of diabetes (e.g., genetic syndromes, secondary pancreatic diabetes, diabetes due to endocrinopathies, drug- or chemical-induced, and post-organ transplant).
- 2. Treatment with glucosidase inhibitor, insulin secretagogues (other than sulfonylureas), glucagon-like peptide 1 (GLP-1) agonists within 3 months prior to Visit 1.
- 3. History of any basal, pre-mix or prandial insulin (greater than 7 days) within 6 months prior to Screening.
- 4. History of >2 episodes of severe hypoglycemia within 6 months prior to Screening.
- 5. History of hypoglycemic unawareness (episodes of severe hypoglycemia with seizure or requiring third party intervention or documented low blood glucose without associated autonomic symptoms)
- 6. Subjects with the following secondary complications of diabetes:
 - a. Active proliferative retinopathy as confirmed by a dilated ophthalmoscopy/retinal photography

- examination performed (by a qualified person as per the country legislation) within 6 months prior to Screening.
- b. Renal dysfunction: $eGFR \le 30 \text{ ml/min/1.73 m}^2$
- c. History of proliferative retinopathy or severe form of neuropathy or cardiac autonomic neuropathy (CAN)
- d. Uncontrolled or untreated severe hypertension defined as systolic blood pressure above or equal to 180 mmHg and/or diastolic blood pressure above or equal to 120 mmHg
- e. Presence of unstable angina or myocardial infarction within 6 months prior to Screening, Grade 3 or 4 congestive heart failure (CHF) according to the New York Heart Association (NYHA) criteria, valvular heart disease, cardiac arrhythmia requiring treatment (other than treated atrial fibrillation), pulmonary hypertension, cardiac surgery, history/occurrence of coronary angioplasty and/or stroke or transient ischemic attack (TIA) within 6 months prior to Screening.
- 7. Subjects with psychiatric disorders which, per investigator judgment, may have impact on the safety of the subject or interfere with subject's participation or compliance in the study.
- 8. Subjects who needed (in the last 12 months) or may require systemic (oral, intravenous, intramuscular) glucocorticoid therapy for more than 2 weeks during the study period.
- 9. Laboratory abnormalities at Screening including:
 - a. C-peptide < 0.7 ng/mL
 - b. Abnormal serum thyrotropin (TSH) levels below the lower limit of normal or >1.5X the upper limit of normal
 - c. Elevated liver enzymes (alanine transaminase (ALT), alanine aminotransferase (AST), alkaline phosphatase) >2X the upper limit of normal.
 - d. Very high triglyceride levels (>600 mg/dL); a single repeat test is allowable.
 - e. Any relevant abnormality that would interfere with the efficacy or the safety assessments during study treatment administration.
- 10. Positive history of active liver disease (other than non-alcoholic hepatic steatosis), including chronic hepatitis B or C, primary biliary cirrhosis, or active symptomatic gallbladder disease.
- 11. Positive history of HIV.
- 12. Use of the following medications:

- a. History of any basal, pre-mix or prandial insulin (greater than 7 days) within 6 months prior to Screening.
- b. Administration of thyroid preparations or thyroxine (except in subjects on stable replacement therapy) within 6 weeks prior to Screening.
- c. Administration of systemic long-acting corticosteroids within two months or prolonged use (more than one week) of other systemic corticosteroids or inhaled corticosteroids (if daily dosage is > 1,000 µg equivalent beclomethasone) within 30 days prior to Screening. Intra-articular and/or topical corticosteroids are not considered systemic.
- d. Use of medications known to modify glucose metabolism or to decrease the ability to recover from hypoglycemia such as oral, parenteral, and inhaled steroids (as discussed above), and immunosuppressive or immunomodulating agents.
- 13. Known allergy to soy.
- 14. Subject is on a weight loss program and is not in the maintenance phase, or subject has started weight loss medication (e.g., orlistat or liraglutide), within 8 weeks prior to Screening.
- 15. Subject has had bariatric surgery.
- 16. Subject is pregnant or breast-feeding.
- 17. Subject is a user of recreational or illicit drugs or has had a recent history (within 1 year of Screening) of drug or alcohol abuse or dependence. (Note: Alcohol abuse includes heavy alcohol intake as defined by >3 drinks per day or >14 drinks per week, or binge drinking) at Screening. Occasional intermittent use of cannabinoid products will be allowed provided that no cannabinoid products have been used during the 1 week prior to each visit.
- 18. One or more contraindications to metformin as per local label.
- 19. History of gastrointestinal disorders (e.g. hypochlorhydria) with the potential to interfere with drug absorption.
- 20. At the Principal Investigator's discretion, any condition or other factor that is deemed unsuitable for subject enrollment into the study.

Statistical Methods

The primary endpoint for this study is the change from baseline in HbA1C at Visit 9 (Part 2 Week 10). Mean change from baseline to Week 12 HbA1C (Visit 9 value – Visit 3 value) will be tested using an analysis of covariance (ANCOVA) model using baseline HbA1c and whether the subject is using additional antidiabetes drugs (beyond Metformin) as covariates.

Observed means and mean changes from baseline for HbA1C and FPG will be analyzed by visit using a method similar to the primary endpoint.

Change from baseline to Week 12 (Visit 9, Part 2 Week 10) in PPG parameters during a MMTT, including AUC₀₋₆₀, AUC₀₋₁₂₀, and 1 & 2-hour PPG absolute levels and excursions will be analyzed using a method similar to the primary endpoint.

Changes from baseline to Week 12 (Visit 9, Part 2 Week 10) in mean 24-hour, mean day time (6 AM to 10 PM) and mean night time (10 PM to 6 AM) glucose as measured by CGM will be analyzed using a method similar to the primary endpoint. For a day to be included in the calculations of the overall means, the subject must have at least 80% of the expected glucose readings.

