8.1 Study Design

The primary analysis is a comparison of change in HbA1c for the ORMD-0801 treated groups and placebo. Let pC be the delta HbA1C for the control (placebo) arm and let pT be the delta HbA1C for the treatment (ORMD-0801) arms. The primary analysis is:

H0: pC=pT

H1: pC < pT

Trial success is defined as rejecting the null hypothesis of no difference in delta HbA1C between active study drug and placebo.

In order to preserve on overall alpha level of 0.05, a stepwise approach will be used for hypothesis testing. The initial hypothesis will be ORMD-0801 TID versus combined placebo. If the initial hypothesis results in a rejection of H0, the secondary test, ORMD-0801 BID versus combined placebo, will take place. If both the initial and secondary hypotheses result in rejections of H0, the third test, ORMD-0801 QHS versus combined placebo will take place.

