8.2 Sample Size

8.2.1 Cohort A

The primary efficacy endpoint is the change from baseline in HbA1C at Visit 9 (Part 2- Week 10) after 12 weeks of active treatment. Based on previous results, a drop in HbA1C of 0.6% is expected with a standard deviation of 1.2. The primary analysis is based on combining the BID and TID treatment regimens together to compare to combined placebo. In order to achieve 80% power, there 48 completers are needed per treatment group.

Assuming an approximate 20% drop out rate, 240 randomized subjects would yield around 192 completers or approximately 48 subjects per treatment group. This would provide 80% power to detect a decrease in HbA1C of 0.6% for the BID and TID active combined versus combined placebo.

An additional 20 non-randomized subjects will be enrolled to receive excipient matched placebo to ensure that the fish oil placebo does not have a significant effect on efficacy or safety. The choice of adding 20 subjects is not based on statistical considerations.

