8.3.1 HbA1C Evaluation

Mean change from baseline to Week 12 HbA1C (Visit 9 value – Visit 3 value) will be tested using an analysis of covariance (ANCOVA) model using baseline HbA1C and whether the subject is using additional antidiabetes drugs (beyond metformin) as covariates.

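### Under the only signed definition of change in the document, the primary alternative in Section 8.1 (pC < pT) points toward harm, and neither the sidedness of alpha nor the direction of success is stated

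*Combined protocol and SAP*

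**What the plan says.** Three parts of the plan bear on the direction of the primary test.

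- **Sign of the change.** The Synopsis (Statistical Methods) says "Mean change from baseline to Week 12 HbA1C (Visit 9 value – Visit 3 value) will be tested". Section 8.3.1 repeats the definition and names the model: "Mean change from baseline to Week 12 HbA1C (Visit 9 value – Visit 3 value) will be tested using an analysis of covariance (ANCOVA) model". In both places a fall in HbA1C is negative.
- **Hypotheses, alpha and success.** Section 8.1 says "Let pC be the delta HbA1C for the control (placebo) arm" and "let pT be the delta HbA1C for the treatment (ORMD-0801) arms". It then sets H0: pC = pT and H1: pC < pT, and attaches no sign to delta. On success it says "Trial success is defined as rejecting the null hypothesis of no difference in delta HbA1C between active study drug and placebo". On error control it says "In order to preserve on overall alpha level of 0.05, a stepwise approach will be used for hypothesis testing". The sequence is TID, then BID, then QHS, each against combined placebo. The plan does not say whether 0.05 is one- or two-sided.
- **Sample size.** Section 8.2.1 says "a drop in HbA1C of 0.6% is expected with a standard deviation of 1.2" and, for 48 completers per group, "This would provide 80% power to detect a decrease in HbA1C of 0.6% for the BID and TID active combined versus combined placebo".

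**The concern.** If delta is the change that Section 8.3.1 analyses, a drug that lowers HbA1C more than placebo has the more negative delta, so benefit is pT < pC. The written alternative is the reverse. It governs the primary endpoint and is carried through all three steps of the sequence.

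The rest of Section 8.1 does not settle the matter. An inequality in H1 suggests a one-sided test, a success rule based on rejecting no difference suggests a two-sided one, and alpha is given without a side. Direction and sidedness could therefore be chosen after the data are seen. If only the inequality were reversed, and 0.05 were then read as one-sided, the chance of falsely declaring benefit would be 5%. Under a two-sided 0.05 test it is 2.5%.

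**Working it through.** **Inputs.** Difference 0.6 and SD 1.2 (Section 8.2.1). 48 completers per group (Section 8.2.1). Allocation 1:1:1:1 with the placebo regimens combined (Section 5.2), so BID and TID combined against placebo is 96 v 48, and a single regimen against placebo is 48 v 48.

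**1. Direction.** With delta = Visit 9 minus Visit 3, a 0.6 benefit is pT − pC = −0.6. H1 as written requires pT − pC > 0. The two are opposite.

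**2. Reproducing the plan's 48.** For k active completers per placebo completer, n(placebo) = (1 + 1/k)(z_α + z_0.80)² × SD²/difference², with SD²/difference² = 1.44/0.36 = 4.

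- Two-sided 0.05, k = 2: 1.5 × (1.960 + 0.842)² × 4 = 47.1, so 48. This matches exactly.
- One-sided 0.05, k = 2: 1.5 × (1.645 + 0.842)² × 4 = 37.1, so 38.
- Two-sided 0.05, k = 1: 2 × (1.960 + 0.842)² × 4 = 62.8, so 63.
- One-sided 0.05, k = 1: 2 × (1.645 + 0.842)² × 4 = 49.5, so 50. This is close to 48.

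The randomized number also follows: 4 × 48 = 192 completers, and 192/0.80 = 240.

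**3. Standard errors.** SE = 1.2 × √(1/n_C + 1/n_T).

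- 96 v 48: SE = 0.2121, and 0.6/SE = 2.828.
- 48 v 48: SE = 0.2449, and 0.6/SE = 2.449.

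**4. Chance of rejection when the true benefit is 0.6.** The normal approximation for 96 v 48 is:

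- two-sided 0.05: Φ(2.828 − 1.960) = 0.807;
- one-sided 0.05 toward benefit: Φ(2.828 − 1.645) = 0.882;
- one-sided 0.05 toward the written H1: Φ(−2.828 − 1.645) = 3.9 × 10⁻⁶.

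The noncentral t figures, used in the rest of this point, are:

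| Test | 96 v 48 | 48 v 48 |
|---|---|---|
| Two-sided 0.05 | 80.2% | 67.9% |
| One-sided 0.05 toward benefit | 87.9% | 78.4% |
| One-sided 0.05 toward the written H1 | 4.1 × 10⁻⁶ | 2.3 × 10⁻⁵ |

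**5. The reverse case.** By symmetry, a true worsening of 0.6 at 96 v 48 would be significant with probability 87.9% under a one-sided 0.05 test toward the written H1, and 80.2% under a two-sided 0.05 test. Either result would meet the success rule as worded.

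**The case against.** Several points on the other side carry weight.

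- **Delta may have meant size of reduction.** Section 8.1 uses a different word from Section 8.3.1 and gives it no sign, and Section 8.2.1 next to it speaks of a drop and a decrease as positive amounts. On that reading H1 points the right way. This is possible, but the document never says so, and the one signed definition it gives says the opposite. Section 8.1 needs an edit on either reading.
- **The plan nowhere says the test is one-sided.** A reader might infer that the trial as planned cannot detect benefit, or that a beneficial drug must fail and a harmful one succeed. The document does not support that. It would follow only if a one-sided test toward the written H1 were run. The success rule has no direction, the ANCOVA is specified without a side, and the sample size matches a two-sided test that detects benefit.
- **The sample size does not settle sidedness beyond doubt.** A reader might also infer that only a two-sided 0.05 test gives 80%. One-sided 0.05 at 48 v 48 gives 78.4%, which is close, and TID against placebo is the first comparison in the sequence. Two-sided 0.05 is the best match for the combined comparison that Section 8.2.1 names, but not the only near one.
- **Intent is clear.** The primary objective is to improve glycemic control, so counting a worsening as success is a literal reading that nobody would have wanted. The rule as worded still permits it.
- **Details are deferred.** The opening of Section 8 leaves further detail to the statistical analysis plan, and the document under review has no separate text that fixes delta or sidedness. A later document may do so. Section 8.1 would still contradict Section 8.3.1.

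**Conclusion.** The inconsistency is real, and the primary hypothesis statement should be corrected. Under the only signed definition of change, H1 in Section 8.1 points toward harm, alpha has no stated side, and success has no stated direction. It is most likely a drafting error.

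The size depends on how the test is run, with a true difference of 0.6, SD 1.2 and 96 v 48 completers:

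- One-sided 0.05 toward the written H1: a true benefit is declared with probability about 4 × 10⁻⁶.
- Two-sided 0.05: a true benefit is detected with 80.2% power, but a significant worsening would also satisfy the success rule.

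The near-zero figure describes the first case only, and the plan does not commit to it. These figures rest on the plan's own effect size, SD and completer numbers, and on a two-sample comparison without covariate adjustment.

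**What to change.** In Section 8.1, and in the SAP to match:

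1. Define delta HbA1C as Visit 9 minus Visit 3, as in Section 8.3.1.
2. State the test as two-sided at 0.05. Equivalently, state H1: pT < pC at one-sided 0.025.
3. Define success at each step of the TID, BID, QHS sequence as a significant result with the adjusted difference pT minus pC below zero.

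Reversing the inequality alone is not enough, because the side of alpha would still be open. The cost is a change of wording, to be made before unblinding. No extra subjects or data are needed, and 48 completers per group stands for the comparison that Section 8.2.1 powers.
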